Hypothesis 1: Objectively measured poor sleep is associated with greater levels of inflammation and markers of cardiopulmonary disease among antiretroviral therapy (ART)-treated people living with HIV (PLWH) compared to those without HIV.

Hypothesis 2: Among ART-treated PLWH, downregulation of the adenosine pathway is associated with objectively measured markers of poor sleep.

Hypothesis 3: Acute sleep deprivation in ART-treated PLWH does not produce a compensatory increase in extracellular adenosine generation and signaling, leading to increased inflammation and endothelial dysfunction.

Study Design & Methods

Research Activities:

Recruitment

Individuals with and without HIV will be recruited through advertising in local longitudinal research cohorts studying PLWH, by advertising through clinics that care for PLWH and patients at high risk for developing HIV, and through platforms developed for recruiting people in the community interested in participating in research. Telephone screening will be performed to assess eligibility and review the study protocol. Individuals who meet eligibility criteria and are interested in participating will be scheduled for an in-person study visit.

Cross-Sectional Protocol

Visit 1

A point-of-care urine pregnancy test will be given to women of child-bearing potential. If the pregnancy test is positive, the participant will be ineligible for the study and procedures will be discontinued. The participant will then be asked to complete a battery of interviewer-administered questionnaires. This battery consists of questions on demographics, education, work schedule, caffeine use, nicotine use, and the reduced Morningness Eveningness Questionnaire (rMEQ) to assess circadian preference. Participants will have a wrist actigraph (Respironics Spectrum) placed on the non-dominant wrist and instructed to wear for two weeks. They will be given instructions

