on pressing the event monitor whenever getting into or out of bed and also asked to complete a sleep diary each morning on awakening. Participants will also be given a wrist device for home sleep apnea testing (Itamar Medical WatchPAT) to place on their dominant wrist to wear for one night while they are sleeping. They will be given instructions for activating and wearing the device as well as proper placement of the fingertip sensor cap. Participants will be asked to return the WatchPAT device at Visit 2 where the data will be downloaded and reviewed. One week after the visit, a staff member will call participants to remind them to continue wearing the actigraph and completing the sleep diary.

Visit 2

Visit 2 will take place as soon as possible at least two weeks after Visit 1. Participants will be instructed to continue to wear the actigraph until this visit and to bring the completed sleep diaries with them to this visit. Actigraphy data will be downloaded and reviewed as will the sleep diaries. If data are incomplete (< one week of complete data), participants will be asked to repeat sleep diary and actigraphy testing. They will be issued a new actigraph and diaries to wear for an additional two weeks and be rescheduled to complete Visit 2 activities described below. Urine will be collected and frozen for adenosine analysis. Phlebotomy will be performed by research staff to obtain 100cc of blood. One tube will be prepared with a solution that specifically blocks adenosine metabolism and the rest will be standard Na-EDTA tubes. A battery of interviewer-administered questionnaires will be administered including: the Pittsburgh Sleep Quality Index, Epworth Sleepiness Scale, Insomnia Severity Index, Munich Chronotype Questionnaire, PROMIS 8a sleep disturbance scale, PROMIS 8b sleep-related impairment scale, eight-item Patient Health Questionnaire, seven-item Generalized Anxiety Disorder screener, Alcohol Use Disorders Identification Test, and the ten-item Drug Abuse Screen Test. At the end of Visit 2, staff will ask permission from HIV+ participants to be contacted at a later date to present the interventional study and discuss possible enrollment.

Interventional Protocol

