Participants will stay awake for the remainder of procedures. Study staff will remain with the participants at all times (except for during bathroom trips) during sleep deprivation to monitor mood and to keep them awake through conversations, playing board games, and watching television. The KSS, PVT, and PANAS will be administered every hour, every two hours, and every four hours, respectively. The participants will again be prepared with limited montage polysomnography equipment described above and will need to remain fasting (except water) starting four hours prior to sleep midpoint until vascular testing is completed (the same time frame as the prior day). In the morning, the participant will provide a urine sample and have 100cc of blood drawn at the same time as the previous day. Vascular testing will be performed as described above, after which breakfast will be served. The KSS, PVT, and PANAS will continue to be administered until seven hours after the participant's normal sleep midpoint time. At this point the participant will be provided the opportunity to have eight hours of recovery sleep, and staff will encourage them to do so for their safety before returning home. They will be allowed to leave without recovery sleep if another adult is able to drive them home.

Eligibility Criteria

Aims 1-2

Inclusion- HIV+

- 18-75 years old
- On contiguous anti-retroviral therapy (ART) regimen for at least 48 weeks
- CD4+ cell count > 200 cells/mm³

Inclusion- HIV- (Aim 1 only)

- 18-75 years old

*Note: HIV- participants are only eligible for participation in Aim 1.

Exclusion- all

- Presence of a significant sleep disorder (restless legs syndrome, narcolepsy, sleep disordered breathing on active treatment)
- Presence of an active chronic inflammatory or autoimmune disease (e.g., scleroderma, Crohn's disease)
- Regular use of medications which would impact assessment of inflammatory markers (systemic glucocorticoids, interleukins, anti-TNF drugs)
- Use of medications impacting adenosine function (theophylline or dipyridamole)
- Any initiation of an investigational/experimental therapy in the prior 30 days
- Current pregnancy

Aim 3

Inclusion

- HIV+
- Completion of Aim 1 with at least 5 days of valid actigraphy data
- On continuous anti-retroviral therapy (ART) regimen for at least 48 weeks
- CD4+ cell count > 200 cells/mm³

Exclusion

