- Atypical sleep patterns (mean sleep duration < 6 hours, sleep efficiency < 85%, standard deviation of sleep duration > 60 minutes, sleep midpoint < 2 a.m., sleep midpoint > 5 a.m.)
- Elevated risk of adverse health effects from sleep deprivation (bipolar disorder, epilepsy, history of suicidal ideation in the past 6 months)
- Heavy caffeine use (>3 caffeinated beverages per day)
- Alcohol abuse
- Drug abuse
- Daily use of medications for treatment of insomnia
- Sleep disordered breathing (AHI >15 on in-lab sleep study)
- Current pregnancy

Statistical Analysis Plan

Hypothesis 1:

The primary exposures will be four domains of sleep health: sleep duration (mean hrs/night during the main rest period), sleep fragmentation index (mean across main rest periods), sleep regularity (interdaily stability over a 14-consecutive day period), and sleep apnea severity (pAHI). Secondary measures will be mean sleep midpoint, mean diary-reported sleep quality, and

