proportion of days with naps. The primary measures of inflammation will be serum IL-6 and sCD14 levels. Secondary measures will include the other 12 cytokines both inflammatory and anti-inflammatory on the Luminex platform including TNF α , CRP, IL-10, and sCD163. All inflammatory biomarkers will be transformed as needed to approximate a normal distribution. Given that some sleep exposures (particularly sleep duration) have U-shaped associations with cardiovascular outcomes, we will initially model sleep exposures in quintiles to assess for non-linear relationships with inflammation measures. If a linear association is confirmed, we will then model sleep exposures continuously to maximize power and use multivariable linear regression to regress IL-6 and sCD14 levels on each of the three sleep exposures among HIV+ subjects. Initial analyses will adjust for age and sex. Alternatively, we will use fractional polynomial regression to test the nonlinear relationship between sleep measures and inflammatory markers. In all models, we will further adjust for CD4+ T cell count and viral load to determine if sleep exposures are associated with inflammation in HIV+ subjects independent of severity of infection. Subsequently, we will generate models including all four sleep exposures simultaneously to understand the independent effects of each sleep domain. If needed, we will apply dimension reduction methods (e.g., principal components analysis) to overcome collinearity in sleep domains. Secondary analyses will utilize structural equation modelling to evaluate the extent to which identified associations represent effects mediated by sleep directly versus effects specific to depression. Furthermore, we will stratify by sex to separately evaluate the association between sleep and inflammation in men and women. Formal testing of effect modification will be performed by including an interaction term in the multivariable models. We will repeat models in HIV- subjects and then test whether HIV infection moderates the association between sleep and inflammation by modeling data from those with and without HIV infection in one model with a sleep by HIV interaction term, using a two-sided $p < 0.05$ as the criterion for rejecting the null hypothesis of no effect modification.

Hypothesis 2:

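### Does the 14-consecutive-day definition of sleep regularity leave a primary exposure undefined for shorter actigraphy records?

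*Combined protocol and SAP*

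**What the plan says.** The SAP, under Hypothesis 1, states: "The primary exposures will be four domains of sleep health". One of the four is "sleep regularity (interdaily stability over a 14-consecutive day period". Duration and fragmentation are means over main rest periods, and apnea severity comes from a one-night home test, so only regularity names a fixed run of days. After single-exposure models, "we will generate models including all four sleep exposures simultaneously".

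The Cross-Sectional Protocol sets the data collection. At Visit 1 the actigraph is "placed on the non-dominant wrist and instructed to wear for two weeks". "Visit 2 will take place as soon as possible at least two weeks after Visit 1", and the device is to be worn until that visit. The completeness rule reads: "If data are incomplete (< one week of complete data), participants will be asked to repeat sleep diary and actigraphy testing". In that case, "They will be issued a new actigraph and diaries to wear for an additional two weeks".

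The Aim 3 inclusion criteria carry a separate threshold: "Completion of Aim 1 with at least 5 days of valid actigraphy data".

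The SAP does not say how interdaily stability is obtained from a record that passes the Visit 2 check but lacks 14 consecutive valid days. It also does not say which recording counts after a repeat.

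**The concern.** The exposure is defined over 14 consecutive days, yet the check that sends a participant on to the rest of Visit 2 is met at 7. Planned wear is 14 days, so a visit held exactly on schedule leaves no spare day, and one missed day breaks the run. Two readings are then possible:

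1. Fourteen valid days are required, and everyone else has no regularity value.
2. Fourteen days is the window, and the valid days in it are used.

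Reading 1 would remove participants from the regularity model and, in a complete-case analysis, from the four-exposure model. The same would follow in the HIV-negative models and the test of the sleep-by-HIV interaction. If the choice were made after the data were in, it could be steered by results. Reading 2 has its own difficulty: interdaily stability is biased upward in short records, so record length could leak into the exposure and its quintiles.

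**Working it through.** **Inputs.** From the documents: window 14 days, planned wear 14 days, repeat threshold 7 complete days, Aim 3 threshold 5 valid days. The documents give no invalid-day rate, sample size or power for this aim. Everything below labelled as assumed is therefore not theirs, and there is no planned figure to reproduce.

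**Which reading the text supports.** The Visit 2 section uses its own term, incomplete, for less than one week of complete data. A record with 7 to 13 complete days is by that term not incomplete, and the participant proceeds. Two weeks of wear matches a 14-day window. Reading 1 is possible from the wording of the exposure alone, but nothing else in the documents supports it.

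**Share without 14 consecutive valid days.** Assume each day is invalid independently with probability q = 2%, 3% or 5%.
- 14-day recording: share complete = (1 − q)^14 = 0.754, 0.653, 0.488, so 25%, 35%, 51% are short.
- 18-day recording (assumed, for a delayed visit): (1 − q)^14 × (1 + 4q) = 0.814, 0.731, 0.585, so 19%, 27%, 41% are short.

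**Reading 1, 14 valid days required.** Interval ratio = 1/√share. Power = Φ(2.80√share − 1.96), taking an assumed 80% power on all accepted participants.

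| Recording | q | Interval ratio | Power |
|---|---|---|---|
| 14 days | 2% | 1.15 | 68% |
| 14 days | 3% | 1.24 | 62% |
| 14 days | 5% | 1.43 | 50% |
| 18 days | 2% | 1.11 | 71% |
| 18 days | 3% | 1.17 | 67% |
| 18 days | 5% | 1.31 | 57% |

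**Reading 2, valid days used.** With D valid days and independent day-to-day noise, the expected value is about IS + (1 − IS)/D. The shift against a full record is (1 − IS)(1/D − 1/14). At an assumed IS of 0.40:
- Short accepted records from a 14-day recording average 12.86, 12.79 and 12.63 valid days. The mean shift is 0.6 × (E[1/D] − 1/14) = 0.0038, 0.0041, 0.0048.
- A record with exactly 7 valid days shifts by 0.6 × (1/7 − 1/14) = 0.043.
- A record with 5 valid days would shift by 0.6 × (1/5 − 1/14) = 0.077.

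Simulated 24-hour profiles agree with the approximation. Mean interdaily stability at 7 against 14 days was 0.394 against 0.347 (long-run 0.3), 0.571 against 0.534 (0.5) and 0.741 against 0.721 (0.7).

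Very short records are rare if invalid days are independent: at q = 5%, the chance of 9 or fewer valid days in 14 is 0.04%.

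**Effect on the regression.** Simulation with 3000 participants, assumed true stability of mean 0.45 and SD 0.12, and an outcome slope of −0.25 SD:
- Independent invalid days: correlation with the full 14-day value 0.997 to 0.999, standard-error ratio 1.00, slope ratio within 1% of 1.
- Clustered non-wear (mean 10% of days, within-person correlation 0.2): 47% short, mean 11.5 valid days among them, shift about 0.01. The standard-error ratio is 1.00 to 1.02 using valid days, against 1.37 (closed form) to 1.40 (simulated) if 14 are required.
- Non-wear tied to the exposure (odds of an invalid day doubling per SD lower regularity, 3% at the mean): standard-error ratio 1.01 and slope ratio 1.01 using valid days, against a standard-error ratio of about 1.37 if 14 are required.

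**Repeat recordings.** A repeat is triggered only when the first record has less than one week of complete data. That first record cannot supply the 14-day window, so the repeat is the natural one to use.

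**The case for a change.** The strongest reply is that the exposure definition says consecutive. A literal analyst would exclude short records, and even 2% invalid days would then cost a quarter of the regularity sample. A written rule costs two or three sentences and would fix the choice before results are seen. This stands as far as it goes: the rule is unwritten, and a literal reading would be expensive. But it would discard data the protocol chose to keep, at a precision cost the analyst would see at once. The precision figures are also least favourable for a recording of exactly 14 days; wear until Visit 2 can lengthen it.

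A second reply is that the shift is not always trivial: about 0.04 at 7 valid days, a third of the assumed between-person SD (0.043/0.12 = 0.36), which could move someone between quintiles. That is true of an individual at the floor. In the scenarios examined it does not carry through to the slope or its standard error.

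A third is that the Aim 3 criterion contemplates Aim 1 completers with as few as 5 valid days, below the Visit 2 threshold. It governs entry to the interventional study, not the Hypothesis 1 exposure. It does show that some very short records are foreseen, for example where a repeat also falls short. How few days suffice for interdaily stability is left to the analyst, and so is the handling of a participant below that minimum in the joint model. This is the part of the concern with most substance. The number affected cannot be derived from the documents.

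**Conclusion.** No change to the plan follows. The SAP omits a derivation detail for one of four primary exposures in a cross-sectional aim, and the protocol's wear period and completeness rule point to the sensible way of filling it: treat 14 days as the window and use the valid days in it. On that reading the mean shift in short records is 0.004 to 0.01, the slope stays within about 1% of its full-record value, and the interval is at most about 2% wider.

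Material loss (intervals 1.15 to 1.43 times wider with a 14-day recording, 1.11 to 1.31 with 18 days) arises only under the less supported reading. These figures rest on assumed invalid-day rates of 2% to 5% (10% in the clustered case) and independent day-to-day noise. The shifts are at a true stability of 0.40, and the regression ratios use the simulated distribution. The conclusion would weaken if records near 7 days or fewer proved common, which nothing in the documents suggests. A sentence on the derivation would be harmless at the next SAP revision, but the analysis does not depend on it.

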We will compare the frequencies of immune cells expressing ectonucleotidases (CD39+ T cells, CD73+ T cells, and CD39+ CD73+ T cells), monocyte adenosine receptor expression (A1R and A2AR), ADO and inosine levels, and measures of T cell activation between those HIV+ subjects with healthy and poor sleep. Ectonucleotidase expression on B cells and monocytes, additional purine pathway metabolites, and frequencies of CD14+ monocytes expressing IL-6 and/or TNF α will also be compared in secondary analyses. Analyses will initially use t-tests for normally distributed variables or Mann Whitney tests for non-normal distributions. Subsequent analyses will consider potential confounders (age, sex, CD4+ T cell count, viral load, habitual caffeine use, chronotype, sleep midpoint) and adjust in multivariable linear regression for the set of variables that differ between the healthy and poor sleep groups at $p < 0.10$. Sex-related differences will be tested by evaluating the statistical significance of a sex * sleep interaction term.

Hypothesis 3:

The primary outcome measures are levels of soluble CD14, soluble CD163, and circulating IL-6 levels. Secondary outcome measures are flow mediated dilation (percent change in brachial artery diameter to reactive hyperemia), monocyte expression of IL-6, monocyte expression of TNF α , frequency of CD4+ T cells expressing HLA-DR and CD38, and frequency of CD8+ T cells expressing HLA-DR and CD38. Additional pre-specified outcomes include plasma adenosine and inosine levels, urinary 3'5'-cAMP, and frequencies of CD4+ and CD8+ T cells expressing CD39

and CD73. The impact of sleep deprivation will be assessed by performing paired t-tests of each of these outcomes comparing baseline to post-sleep deprivation values. For variables with non-normal distributions, we will either transform variables or use Wilcoxon signed-rank tests. The correlation between the changes in each domain (expressed as percent change from baseline) will be calculated to assess the extent to which change in endothelial function may be predicted by change in inflammation or ADO signaling and change in inflammation by change in ADO signaling. Secondary analyses will consider the extent to which sex, CD4+ T cell count, and viral load impact sensitivity to sleep deprivation by regressing each of these potential effect modifiers on the percent change in each of the primary outcome measures for inflammation, endothelial function, and ADO signaling.

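### Hypothesis 1 leaves nicotine use and AUDIT score out of every model although both are collected in both HIV groups, so the within-group sleep slopes may be confounded; a side-by-side sensitivity model would show by how much.

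*Combined protocol and SAP*

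**What the plan says.** **Adjustment set (SAP, Hypothesis 1).** The first models are limited: "Initial analyses will adjust for age and sex". The next step is "In all models, we will further adjust for CD4+ T cell count and viral load", which the text ties to severity of infection in HIV+ participants. Later models put all four sleep domains in together. Sex is also handled by stratification and an interaction term. A secondary structural equation model is planned "to evaluate the extent to which identified associations represent effects mediated by sleep directly versus effects specific to depression". The models are then repeated in HIV- participants, and moderation is tested by "modeling data from those with and without HIV infection in one model with a sleep by HIV interaction term" at two-sided p < 0.05. No Hypothesis 1 model names nicotine or alcohol.

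**Data collected (Cross-Sectional Protocol).** At Visit 1, "This battery consists of questions on demographics, education, work schedule, caffeine use, nicotine use" and a circadian preference scale. The Visit 2 questionnaires include the "Alcohol Use Disorders Identification Test, and the ten-item Drug Abuse Screen Test". Both visits belong to the protocol that HIV+ and HIV- participants share.

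**Eligibility (Aims 1-2).** One exclusion is "Regular use of medications which would impact assessment of inflammatory markers". Nothing in the list concerns nicotine or alcohol. Alcohol abuse is an exclusion for Aim 3 only.

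**Hypothesis 2, for comparison.** "Subsequent analyses will consider potential confounders (age, sex, CD4+ T cell count, viral load, habitual caffeine use, chronotype, sleep midpoint". That list is longer and includes caffeine, but it also omits nicotine and alcohol.

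**The concern.** Exposure is not assigned in Hypothesis 1, so the meaning of a sleep slope depends on what is held constant. CD4+ count and viral load describe HIV disease; they do not stand in for behaviour. A person who uses nicotine or drinks heavily may both sleep worse and have higher inflammatory markers. If so, part of the slope credited to sleep belongs to that use, in HIV+ and HIV- participants alike. The information needed to check this will be in the database, but the plan does not call for it. If it is added only after results are known, the choice of covariates is open to the charge that it followed the answer.

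**Working it through.** **1. Is the omission real?** The quoted sentence covers only the initial models, so each later step has to be read too. CD4+ count and viral load, mutual adjustment of sleep domains, the depression model, the sex strata and interaction, the HIV- repeat and the pooled model add neither variable. Eligibility does not close the gap, because Aims 1-2 restrict neither.

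**2. Is there a plan figure to reproduce?** No. The documents give no sample size, power or detectable effect for Hypothesis 1, and nothing on how nicotine or alcohol relates to sleep or the markers. Every input below is an assumption, taken as conditional on the planned covariates.

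**3. Bias in a within-group slope.** Sleep and marker are in SD units and the true slope is 0. For nicotine, with a proportion p of users, a marker b SD higher in users and correlation r between use and sleep, bias = b × r × √(p(1−p)). With p = 0.4, √(0.4 × 0.6) = 0.490. For AUDIT, with g the marker change in SD per SD of AUDIT, bias = g × r.

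| Inputs | Nicotine | AUDIT | Sum |
|---|---|---|---|
| Low: b 0.3, g 0.05, r 0.1 | 0.015 | 0.005 | 0.020 |
| Mid: b 0.4, g 0.1, r 0.2 | 0.039 | 0.020 | 0.059 |
| High: b 0.5, g 0.15, r 0.3 | 0.073 | 0.045 | 0.118 |

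**4. False-positive rate, nicotine alone.** With a standard error of about 1/√n, the rejection rate is P(|Z + bias × √n| > 1.96). At mid inputs and n = 200 the shift is 0.0392 × 14.14 = 0.554, which gives 8.6%.

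| n per group (assumed) | Low | Mid | High |
|---|---|---|---|
| 100 | 5.3% | 6.8% | 11.4% |
| 200 | 5.5% | 8.6% | 18.0% |
| 400 | 6.0% | 12.3% | 31.2% |

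**5. Simulation with both variables omitted, then included** (200 per group, 4,000 runs, no true sleep effect, planned HIV+ covariates always in the model). At mid inputs rejection was 13.2% without the two variables and 4.4% with them; the mean slope was 0.060, then 0.001. At low inputs rejection was 5.5%, then 4.9%.

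**6. A second parameterisation.** For one binary confounder, bias = p(1−p) × b × d, with d the sleep difference in SD between users and non-users. At p 0.30, b 0.4, d 0.3 this is 0.21 × 0.12 = 0.025. The rejection rate is then 6.5% at n = 200, with a range of 5.0% to 18.3% over p 0.15–0.45, b 0.2–0.6 and d 0.1–0.5.

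**7. The sleep-by-HIV term.** Its bias is the difference between the two within-group biases, so it is 0 if p, b and d are equal. If prevalence were 0.45 in one group and 0.15 in the other (b 0.4, d 0.3), it would be 0.0297 − 0.0153 = 0.014.

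**8. Precision cost.** The largest loss arises if both variables correlate r with sleep and c with each other, and neither affects the marker. Then R² = 2r²/(1+c) and the SE factor is 1/√(1−R²). With c = 0.158 (assumed), the factor is 1.009 at r = 0.1, 1.036 at r = 0.2 and 1.088 at r = 0.3. Simulations of the r = 0.3 case gave 1.07 to 1.10. In the pooled model with four added terms, the simulated factor for the sleep-by-HIV term ran from 0.96 to 1.10.

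**The case against.** The strongest reply is that Hypothesis 1 is comparative. Its only test with a stated criterion is the sleep-by-HIV term, and that term is unbiased if the groups are alike. This stands. The within-group slopes are nonetheless planned in each group and will be interpreted, so the point survives for them.

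Second, the documents do not say that nicotine or alcohol relates to sleep or to the markers. This also stands: the slopes may be confounded; they have not been shown to be. A reader might infer from Aim 3's abstinence rule at Visit 5 that the plan itself treats both as confounders. It does not support that. The rule gives no reason and concerns a two-day visit, not habitual use. Nor is the plan inconsistent on these two variables, since the Hypothesis 2 list omits them as well.

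Third, 18.0% is a corner case. With 40% users, r = 0.3 means a sleep difference of 0.3/0.490 = 0.61 SD between users and non-users, beyond the 0.5 SD used as the top of the second calculation. The mid value is the fairer summary.

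Fourth, use may partly result from poor sleep, so that adjusting for it removes some of the effect of interest. If use results wholly from poor sleep, the amounts in the first table are an indirect effect of sleep and not bias. This stands, and it is why the added model should accompany the planned one and not replace it.

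**Conclusion.** The omission is a matter of record. Its consequence is conditional: if nicotine use or AUDIT score relates to both sleep and the markers, the planned within-group slopes are confounded. The direction and size cannot be fixed from the documents. At an assumed 200 per group, nicotine alone takes a nominal 5% slope test to about 8.6% at mid inputs, and from 5.5% to 18.0% across the assumed range; the low end is negligible.

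A reader might go further and conclude that the sleep-by-HIV test is biased. That would need use, or its relation to sleep or to the marker, to differ by HIV status, and the documents do not show this. The point is a cheap improvement: a sensitivity analysis of modest priority, not a fault that invalidates Hypothesis 1.

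**What to change.** Pre-specify one additional sensitivity model in the SAP for Hypothesis 1:

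- Within each HIV group, add current nicotine use (yes/no) and AUDIT total score (continuous) to the planned covariates.
- In the pooled model, add both variables with their HIV interactions (four terms).
- Name the base covariates for the HIV- models and for the pooled model. The SAP does not list them separately, and its instruction to adjust all models for CD4+ count and viral load leaves the HIV- set unclear.
- Fit the models with and without the added terms on the same participants. The two variables come from different visits, so missing answers could otherwise change the sample, and a shift in the slope could not be credited to the added terms.
- Report the two side by side, stating that use may partly result from poor sleep and that the added model may over-adjust.
- Say whether caffeine use and the DAST-10, also collected, enter the model, and why.

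**Cost.** SAP wording only; no new data. The within-group standard error of the sleep slope rises by at most about 9% under the assumed inputs (both variables correlated 0.3 with sleep and 0.158 with each other, neither affecting the marker), and usually much less. The worst simulated rise for the sleep-by-HIV term was about 10%. Over-adjustment remains possible, and the side-by-side report makes it visible.
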